## Materials

For the mindful breathing exercise, a 10 min segment from “Guided Meditation Journey into Body Sensations” (retrieved from <https://youtu.be/1cPWV0Sgwi8?t=172>) was used. It aimed to bring participants into a mindful state via a guided breathing exercise. For the control condition, an alternative 10 min clip, “Zen – Jerome Bixby” (retrieved from [https://youtu.be/zUKR\\_3WrE-Y](https://youtu.be/zUKR_3WrE-Y)) was played for participants instead of the guided meditation clip. For comparability with the breathing exercise, the clip includes sound accompanied by a still picture only (i.e., without a moving visual component). Both clips were used in Van Wagenen's (2022) study. As a manipulation check, each participant was given a single 4-point Likert scale item question asking: *“How mindful do you feel right now?”* (1 = *not at all mindful*; 4 = *very mindful*) which was presented after the clips and again after the participant completed the picture description task.

Speech fluency was measured from a picture description task that included photographs similar to those used by Castro and James (2014). Three pictures were taken from the Open Affective Standardized Image Set (OASIS; Kurdi et al., 2017; <https://db.tt/yTZYCga>) and shown to both the intervention and control groups. Three pictures used were: “car crash,” which depicts two cars that have collided with each other and policemen walking around in the background; “cemetery,” which presents a scene in which a woman is seen kneeling down in front of a gravestone and American flags are planted throughout the cemetery; and “couple,” which shows a couple sitting on a bench overlooking a lake with the man facing the lake and the woman sitting with her back turned toward the man, facing the camera, and appearing to be upset (OASIS pictures labeled Car Crash 3, Cemetery 5, and Couple 3; Kurdi et al., 2016). These pictures have ratings data indicating they have negative content, which has been shown to increase disfluencies during picture description tasks (Castro & James, 2014).

A consent form outlining general information as well as risks and benefits of the current study, and the option for withdrawal from the study, was provided to each participant. A fill-in demographics

questionnaire assessing race/ethnicity, education level, age, and gender was used. Additionally, participants' English vocabulary knowledge was assessed using the Shipley (1940) Vocabulary Test. This test contains a total of 40 vocabulary words that participants pair with the corresponding synonym from the four choices given for each word. Finally, a debriefing sheet containing information about the true purpose of the study was used.

### **Procedure**

The study was approved by the UCCS Institutional Review Board. Recruitment took place via the UCCS psychology department SONA system research pool, by distributing flyers throughout the community, and via Research Match ([www.researchmatch.org](http://www.researchmatch.org)) to recruit a wide variety of participants.

Each participant was randomly assigned to either the control ( $N = 32$ ) or intervention group ( $N = 31$ , after excluding the person who did not meet the age inclusion criterion) and given the consent form. Next, the participant saw either the mindful breathing or control clip and then was administered the single question mindfulness measure. Then, each participant was instructed to describe each picture during a 30 – 60 s time frame with research assistants prompting the participant to add more details if they spoke for fewer than 30 s. The three pictures were presented in random order for each participant. Following Van Wagenen (2022), the participant's hand gesturing during the speech fluency task was restricted using an empty water bottle that the participant held with both hands in camera view for the duration of the picture description task. Immediately after the picture description task, mindfulness was re-measured using the 4-point Likert scale.

The first part of the study was conducted via video conference through Zoom, and it was completed within 30-40 min. The researcher carefully monitored each participant's hand gesturing throughout the picture description task and ensured they did not engage in other distracting activities (e.g., leaving the room, using their phone, watching videos, or eating) via the webcam. The researchers carefully read the instructions verbatim from a script and monitored the participant throughout the

video call. If necessary, notes were taken to describe any testing situation deemed as “different” based on the participant’s behavior or other events (e.g., not looking at the screen; looking around as a sign of distraction; interruptions to testing). The picture description task was audio recorded (with the participant’s consent) and was later transcribed to score speech fluency.

After the picture description task, the participant was directed to complete a series of questionnaires and scales on their own via Qualtrics. This information and further instructions were provided by the researcher at the Zoom meeting. The questionnaires included demographic information as well as the Shipley (1940) Vocabulary Test. Additionally, the State-Trait Anxiety Inventory (STAII; Spielberger, 1983), the Kentucky Inventory of Mindfulness Skills (KIMS; Baer et al., 2004), and the Applied Mindfulness Process Scale (AMPS; Li et al., 2016) were administered. These scales will be used as part of a larger study including older adult participants and were not analyzed as part of the current project. These scales required about 10-20 min to complete in total. Finally, a debriefing with an explanation of the true nature of the study was given to each participant.

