Cover Page for Analysis Plan Document

Official Study Title: What makes people better at describing photographs?

NCT05444114

Document Date 5/30/24

Improved speech fluency was operationally defined as increased speech rate, reduced mid-phrase and other speech fillers, and decreased repetitions, repairs/false starts, and omissions.

Speech was transcribed from the recordings by a research assistant, and transcripts were checked by at least one researcher, with any discrepancies reconciled by a third researcher before the transcript was considered final. For the current study, only the main block of speech (e.g., the speech produced before any interjection by the researcher prompting the participant to add more details) was considered for analyses. Next, scoring was completed by a researcher. The number of words the participant produced for each picture description were counted. Following Metz and James (2019), the word count included speech fillers (e.g., *um, uh, hmm*), repetitions (e.g., *"um, the- the time. . ."* counted as four words), and repairs/false starts (e.g., *"the- some of the"*). Non-linguistic sounds such as laughter or lip smacks were not included in the word count. Total time each participant spent speaking (s) was then measured from each recording. Next, speech fillers were counted separately by location. Fillers in the middle of a phrase (e.g., *"the, uh, place I like best"*; *"he is, um, just sitting there"*) were totaled, as were fillers in all other locations. Finally, repetitions, repairs/false starts, and omissions were counted individually and then summed together to yield the number of total disfluencies.

Speech rate was computed by dividing the number of words spoken by the duration of the description (s). Filler words (mid-phrase and other fillers) were counted separately and calculated as a proportion of words spoken. Similarly, total disfluencies were calculated as a proportion of words spoken. Then, a mixed ANOVA was conducted for each dependent variable (speech rate, mid-phrase fillers, other fillers, and total disfluencies) with condition as the independent groups variable and picture as the repeated measure to determine if speech was more fluent in the mindful breathing than in the control condition. No main effect or interaction was expected for pictures, but we reasoned that it would be valuable to know whether similar effects of mindful breathing were found for all pictures.

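### Picture order is randomised but serial position is left out of the mixed ANOVA; a practice or fatigue trend, if there is one, would cost the picture and condition-by-picture tests some power

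*Protocol*

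**What the plan says.** Everyone describes the same three pictures (Protocol, Materials), in an order drawn separately for each person: "The three pictures were presented in random order for each participant". The groups are 32 control and 31 intervention participants (Protocol, Procedure). Each person sees one 10 min clip before the first picture. A single-item mindfulness rating follows the clip, and the Procedure adds: "Immediately after the picture description task, mindfulness was re-measured using the 4-point Likert scale". Materials describes both ratings as a manipulation check.

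In the SAP "a mixed ANOVA was conducted for each dependent variable", "with condition as the independent groups variable and picture as the repeated measure". Those are the only two factors named. Neither document mentions presentation order, serial position, or a condition-by-position term in the analysis. On the picture terms the SAP says "No main effect or interaction was expected for pictures", but gives as its reason for examining them the wish to know "whether similar effects of mindful breathing were found for all pictures".

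**The concern.** Serial position is a factor that the design itself randomises. Practice or tiring over three successive descriptions could shift speech rate or disfluency from the first to the third. Such a shift cancels from each person's average, because everyone occupies all three positions. It does not cancel within a picture: one person describes the cemetery first and another describes it last. In a model without position, that difference is counted as unexplained within-person variation, and it enlarges the denominator of the picture and condition-by-picture F tests.

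What is at stake is how a null interaction is read. The authors expect no interaction and want to know whether the breathing effect is alike across pictures, so a non-significant test is easily taken as evidence of similarity. Avoidable noise pushes the test towards that result. A related gap is that the plan has no term that would show whether the effect of one clip weakens over the task.

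**Working it through.** The documents state no sample size calculation, power, alpha, SD, correlation or position effect, so there is no figure of the plan's own to reproduce.

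**Inputs from the documents.** n = 32 and 31 (63 in total); k = 3 pictures; random order per participant; model with condition and picture only.

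**Assumptions.** Two-sided alpha 0.05; normal outcomes with total SD 1 and correlation 0.5 between pictures, so the within-person variance is 0.5; a condition effect of 0.5, 0.5 and 0 SD on the three pictures; a linear position trend of s within-person SD per step, the same in both arms.

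**Step 1: error inflation.** Give the positions the values −s, 0 and +s in random order. For any one picture the position contribution has variance 2s²/3, and for any two pictures the covariance is −s²/3. The within-person error gains variance minus covariance: 2s²/3 + s²/3 = s². The multiplier is 1 + s².

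**Step 2: interaction power without position.** The effects 0.5, 0.5 and 0 have mean 1/3, so the squared deviations sum to 1/36 + 1/36 + 4/36 = 1/6. The noncentrality is

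λ = (32 × 31 / 63) × (1/6) / [0.5 × (1 + s²)] = 15.746 × 0.3333 / (1 + s²) = 5.249 / (1 + s²).

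The test has 2 numerator df and (63 − 2) × 2 = 122 error df.

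| s | 1 + s² | λ | Power without position |
|---|---|---|---|
| 0 | 1.00 | 5.25 | 51.4% |
| 0.1 | 1.01 | 5.20 | 51.0% |
| 0.2 | 1.04 | 5.05 | 49.7% |
| 0.3 | 1.09 | 4.82 | 47.8% |
| 0.5 | 1.25 | 4.20 | 42.4% |
| 0.7 | 1.49 | 3.52 | 36.3% |

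**Step 3: power with position.** Error df fall from 122 to 120, and a little information is lost because random order leaves position slightly unbalanced across arm and picture. Power is about 50–51% at every s. The gain is nil at s = 0.1, about 1 point at 0.2, 2–3 points at 0.3, about 8 at 0.5 and about 14 at 0.7. With no trend, adding position costs about 1 point.

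**Step 4: a second scenario.** With an interaction sized for 80% power when there is no trend, power without position is 77%, 70% and 49% at s = 0.25, 0.5 and 1.0. In simulation (2,000 trials per setting) the error mean squares without position were 1.06, 1.25 and 2.00, as the formula predicts. With position they returned to about 1.00, and power was 78–80%.

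**Step 5: what is untouched.** With no true interaction, the interaction and picture tests without position rejected in 4.3% to 5.9% of simulated trials. Adding a common trend changed participants' means by no more than rounding error (2 × 10⁻¹⁶), so the condition main effect is the same with or without it.

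**Step 6: a fade in one arm.** Suppose only the breathing arm drifts, by 0.5 SD per step. About half the error df carry the extra 0.25, giving 1 + 0.25/2 ≈ 1.12. Position alone fits the average slope and leaves about ±0.25 per step in each arm: 1 + 0.25² ≈ 1.06. Adding condition-by-position brings it to 1.00. Simulation gave 1.12, 1.06 and 1.00.

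**The case against.** The strongest reply is that the design already deals with order. Randomising it per participant prevents picture from being confounded with position, the planned ANOVA is valid, and leaving out a randomised nuisance factor is common practice. The question the trial was run to answer is the condition main effect, which position does not touch. All of that stands.

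It is also fair that the size depends on chosen inputs. Trends of 0.3 to 0.7 SD per step mean a first-to-third shift of 0.6 to 1.4 SD over three descriptions of 30–60 s each, which may be more than such a short task produces. The power figures treat the outcomes as normal, whereas three of the four are proportions of words. This also stands, and it limits the point to a conditional one.

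A reader might infer three stronger things that the documents do not support:

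- **That order data are in hand.** The Procedure says order was random and the task was audio recorded. It does not say that order was logged. Recovery from the recordings is likely, but that is an inference.
- **That the second mindfulness rating commits the plan to modelling a fade in fluency.** It is presented only as part of a manipulation check.
- **That adding position deals with fading.** Step 6 of the working shows that it does so only in part.

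What survives the reply is narrower. The SAP sets itself a question about similarity across pictures, and the analysis of that question leaves out a factor that could be adjusted for at almost no cost.

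**Conclusion.** The point holds as a low-severity improvement. The omission is plain in the text, and its effect is confined to the error term of the picture and condition-by-picture tests. It would be tempting to conclude that the comparison of breathing with control is biased or that false-positive rates are inflated. Neither follows: a common trend cancels from the condition effect, and type I error stays near 5%. Nor can it be said as fact that the plan loses power, since no position trend is documented.

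Under the assumptions stated in the working, the loss is about 1 point or less up to 0.2 within-person SD per step, 2–3 points at 0.3, and about 8 and 14 points at 0.5 and 0.7. The 51% starting power is itself a product of the assumed 0.5, 0.5, 0 pattern and is not a property of the trial. Whether a fade in the breathing effect exists cannot be told from the planned model.

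**What to change.** Take the serial position of each description from the session records or, failing those, from the audio recordings. For each outcome, fit a linear mixed model with condition, picture, condition-by-picture and position (three levels) as fixed effects and a random intercept for participant. Report it at least as a sensitivity analysis beside the planned picture and condition-by-picture tests.

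To examine fading, add condition-by-position and label it exploratory.

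Whatever model is used, report the condition effect for each picture with confidence intervals, so that a non-significant interaction is not read as proof of similarity.

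Cost: 2 error df for position (122 to 120) and 2 more for condition-by-position (120 to 118); the work of recovering order; and one additional exploratory test for each of the four outcomes, which should be acknowledged as such. Both documents describe the study in the past tense, so if the data have already been analysed the additions should be labelled post hoc.

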Cover Page for Analysis Plan Document

Official Study Title: What makes people better at describing photographs?

NCT05444114

Document Date 5/30/24

Improved speech fluency was operationally defined as increased speech rate, reduced mid-phrase and other speech fillers, and decreased repetitions, repairs/false starts, and omissions.

Speech was transcribed from the recordings by a research assistant, and transcripts were checked by at least one researcher, with any discrepancies reconciled by a third researcher before the transcript was considered final. For the current study, only the main block of speech (e.g., the speech produced before any interjection by the researcher prompting the participant to add more details) was considered for analyses. Next, scoring was completed by a researcher. The number of words the participant produced for each picture description were counted. Following Metz and James (2019), the word count included speech fillers (e.g., *um, uh, hmm*), repetitions (e.g., *"um, the- the time. . ."* counted as four words), and repairs/false starts (e.g., *"the- some of the"*). Non-linguistic sounds such as laughter or lip smacks were not included in the word count. Total time each participant spent speaking (s) was then measured from each recording. Next, speech fillers were counted separately by location. Fillers in the middle of a phrase (e.g., *"the, uh, place I like best"*; *"he is, um, just sitting there"*) were totaled, as were fillers in all other locations. Finally, repetitions, repairs/false starts, and omissions were counted individually and then summed together to yield the number of total disfluencies.

Speech rate was computed by dividing the number of words spoken by the duration of the description (s). Filler words (mid-phrase and other fillers) were counted separately and calculated as a proportion of words spoken. Similarly, total disfluencies were calculated as a proportion of words spoken. Then, a mixed ANOVA was conducted for each dependent variable (speech rate, mid-phrase fillers, other fillers, and total disfluencies) with condition as the independent groups variable and picture as the repeated measure to determine if speech was more fluent in the mindful breathing than in the control condition. No main effect or interaction was expected for pictures, but we reasoned that it would be valuable to know whether similar effects of mindful breathing were found for all pictures.

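### Do per-word proportions from a pre-prompt block with no minimum length call for a length comparison or a different model?

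*SAP*

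**What the plan says.** The protocol's Procedure section sets a target length: "each participant was instructed to describe each picture during a 30 – 60 s time frame". It enforces the lower end by prompting, with "research assistants prompting the participant to add more details if they spoke for fewer than 30 s".

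The SAP (which has no numbered sections) then limits scoring to "only the main block of speech (e.g., the speech produced before any interjection by the researcher prompting the participant to add more details". A prompted description therefore enters the analysis as a block of under 30 s, and no minimum in words or seconds is given.

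Fillers are split by location: those inside a phrase "were totaled, as were fillers in all other locations". The SAP then scales both counts: "Filler words (mid-phrase and other fillers) were counted separately and calculated as a proportion of words spoken". The sum of repetitions, repairs and omissions is likewise divided by the word count. Speech rate is words over seconds. On duration the SAP says: "Total time each participant spent speaking (s) was then measured from each recording".

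The analysis is stated as follows: "a mixed ANOVA was conducted for each dependent variable (speech rate, mid-phrase fillers, other fillers, and total disfluencies"), with condition between participants and picture within. Block length and prompting are not among the dependent variables. No weighting by length or covariate for length is described.

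**The concern.** Block length is set by the participant after the clip has been shown, so the intervention could change it. Its word count is the denominator of three of the four outcomes, and the ANOVA gives a ten-second block the same weight as a sixty-second one. Two harms seem possible.

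- **Noise.** Very short blocks give coarse proportions, so power might be lost.
- **Interpretation.** If some fillers occur once per description whatever its length, the condition that says less shows a higher proportion although later speech is no less fluent. A difference, or its absence, could then be credited to mindful breathing when it reflects how long people talked.

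No planned output would show the reader whether the arms were scored on similar amounts of speech.

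**Working it through.** **Inputs from the documents.** 32 control and 31 intervention participants, three pictures each, and a prompt below 30 s (Protocol, Procedure). The outcome definitions and the model come from the SAP. Neither document states alpha, power, filler rates, block lengths or the share of descriptions prompted, so there is no plan figure to reproduce. Everything else below is assumed, with two-sided alpha 0.05.

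**1. Coarseness of one block.** At 2.3 words/s and a 4% rate, SE = sqrt(0.04 × 0.96 / words):

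| Block | Words | One filler equals | SE (percentage points) |
|---|---|---|---|
| 10 s | 23 | 4.3% | 4.1 |
| 30 s | 69 | 1.4% | 2.4 |
| 60 s | 138 | 0.7% | 1.7 |

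Short blocks are noisier. What matters is whether this harms the comparison of conditions.

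**2. Validity.** With three pictures per person, the ANOVA's condition test equals a t-test on each person's mean of three proportions. Simulation used 4,000 trials per setting, so the Monte Carlo SE is about 0.3 points at 5%. Settings were 2.5 words/s; event rates of 1-8%; between-person CV 0.6 or 1.0; and 0, 30 or 50% of blocks lasting 10-30 s, the rest 30-60 s.

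- Null rejection was 4.2-5.4% over 40 settings.
- With intervention blocks 20-40% shorter it was 4.4-5.7%.
- For the picture-by-condition test it was 4.0-5.7%.

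A second simulation let prompting differ by arm (control versus intervention), with a constant 4% rate. Rejection was 5.0% at 30% v 30%, 5.4% at 50% v 30%, 4.9% at 50% v 10%, and 5.4% at 70% v 10%, with no shift in the mean.

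**3. Precision.** The alternative tested was a negative binomial count model on each person's totals, with a log(words) offset and a permutation p-value. Compared with the ANOVA, its power differed by:

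- -0.3 to +1.3 points (mean 0.4-0.5) if all blocks last 30-60 s;
- 0.0 to +5.0 points (mean 1.0-1.9) if 30-50% are short. The largest gain was from 0.706 to 0.756.

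**4. The opening-filler mechanism.** Let q be the share of descriptions that open with a filler, r the later rate and w the words. The expected proportion is roughly r + q/w. With 30% short blocks, mean length is 0.3 × 20 + 0.7 × 45 = 37.5 s, and 37.5 × 2.5 gives about 94 words. Blocks 20% shorter have about 75 words and blocks 40% shorter about 56.

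- q = 0.5, r = 0.02: 0.0253 at 94 words, 0.0267 at 75 and 0.0289 at 56. The ratios to 94 words are 1.05 and 1.14.
- q = 0.25, r = 0.04: 0.0427, 0.0433 and 0.0445. The ratios are 1.02 and 1.04.

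Simulated ratios for the first case are 1.063 and 1.167. They are a little higher because the ANOVA averages proportions, and the mean of 1/w exceeds 1 over the mean of w. Over the range simulated (q 25-50%, r 2-4%), rejection was 3.8-5.3% at equal lengths, 4.6-7.0% at 20% shorter and 5.9-14.9% at 40% shorter.

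**5. Would the offset model cure this?** It also estimates fillers per word, so r + q/w applies to it too. In the worst setting (q = 0.5, r = 0.02, 40% shorter), one simulation gave rejection of 15.3% for the ANOVA and 12.8% for the offset test, with ratios of 1.16 and 1.14. A second gave 17% and 14%, with ratios of 1.17 and 1.15. The offset model would largely agree with the ANOVA and offer false reassurance.

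**The case for a change.** The strongest case for acting is that the 30-60 s instruction does not secure comparable blocks, since the main-block rule removes whatever the prompt elicited. Randomisation does not secure them either, because length arises after the clip. With one fixed filler per block and large differences in prompting, the second simulation gave rejection of 7.6% (50% v 30%), 15.2% (50% v 10%) and 27.1% (70% v 10%), with mean shifts of 0.3 to 1.0 percentage points. With half a filler per block the figures were 5.8%, 7.5% and 10.3%. A table of words, seconds and prompted share by condition would cost little.

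The reading of the documents stands, and so does the caveat on interpretation. Four things limit it.

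- These rejection rates are not type I error. If the intervention shortens speech and so raises fillers per word, the outcome as defined does differ between arms. The question is what the difference means.
- The mechanism shown concerns fillers outside a phrase. The SAP already scores mid-phrase fillers separately, and no comparable mechanism is shown for them or for total disfluencies.
- A table with equal lengths would dismiss the worry. One with unequal lengths would not confirm it, because that needs the position of the fillers.
- The SAP is a short methods extract in the past tense, so a descriptive table that goes unmentioned may still have been made.

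**Conclusion.** No change to the plan follows. Scoring only unprompted speech is a fair trade-off: it keeps researcher-elicited talk out of the outcome and accepts some short blocks in return. Dividing by words is already a length adjustment, and the task instructions were the same in both arms. The condition test holds close to its nominal 5% for the outcomes as defined, and the precision forgone averages under 2 points of power in the settings tried.

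What remains is a caution in reading one outcome, fillers outside a phrase. If many descriptions open with a filler and one arm speaks markedly less, that proportion moves by 1-6% (20% shorter) or 5-17% (40% shorter) through length alone. With equal lengths the effect vanishes, and nothing in the documents suggests that the arms differed. All these sizes rest on assumed rates, lengths and prompting shares.

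The team may choose to report lengths and prompting descriptively. Words per description are already counted; prompt status and main-block seconds may need checking against the recordings, because the SAP lists no prompt count and does not expressly restrict speaking time to the main block. Analysts would naturally apply the main-block rule to both words and seconds. That is a choice about reporting, and the planned conclusions do not depend on it.

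### Does the SAP need a covariate-adjusted condition effect, given that vocabulary and age are collected and no speech is sampled before the clip?

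*SAP*

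**What the plan says.** The SAP's analysis text (unnumbered) says: "Then, a mixed ANOVA was conducted for each dependent variable". The outcomes are speech rate, mid-phrase fillers, other fillers and total disfluencies. The model is set up "with condition as the independent groups variable and picture as the repeated measure". No covariate and no adjusted or sensitivity estimate is named.

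The Protocol, under Procedure, gives the order of events: random assignment and consent, the clip, a one-item mindfulness rating, the picture descriptions, and the rating again. No speech is sampled before the clip. The group sizes are 32 control and 31 intervention, the latter "after excluding the person who did not meet the age inclusion criterion". Recruitment used a student pool, community flyers and a research registry "to recruit a wide variety of participants".

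On possible covariates, Materials describes a demographics "questionnaire assessing race/ethnicity, education level, age, and gender was used" and a 40-word vocabulary test. Procedure places both late in the session: "After the picture description task, the participant was directed to complete a series of questionnaires and scales on their own via Qualtrics". It adds: "The questionnaires included demographic information as well as the Shipley (1940) Vocabulary Test". The anxiety and mindfulness scales come next, followed by: "These scales will be used as part of a larger study including older adult participants". That sentence, which goes on to say they were not analysed here, most naturally covers those three scales and not vocabulary or age.

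**The concern.** Picture varies within a person, but the study question concerns condition, which varies between people. The condition effect is therefore tested against person-to-person differences in speech, on 61 error degrees of freedom. Recruitment was broad, no stratification is described, and there is no pre-clip speech measure to absorb those differences. Vocabulary could plausibly relate to how people describe pictures, and both it and age are already in hand with no stated analytic use. The plan may therefore seem to forgo precision and to leave a chance imbalance between arms unexamined. In a trial of 63 people, either could matter to how the condition effect is read.

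**Working it through.** The documents give no alpha, effect size, SD or covariate-outcome correlation, so the plan has no figure to reproduce. The only inputs from the documents are the group sizes (Protocol, Procedure): 32 + 31 = 63. Assumptions: two-sided alpha 0.05, complete data, roughly normal participant means, and a joint correlation r of vocabulary and age with the outcome between 0 and 0.5.

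**1. Is the unadjusted comparison valid?** With complete data, the condition test in the mixed ANOVA is the two-sample t test on each participant's mean over the three pictures, with 63 - 2 = 61 df. Condition is randomised, so leaving out covariates does not bias the contrast.

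**2. How large is chance imbalance?**
- The arm difference in a standardised covariate has SD sqrt(1/32 + 1/31) = 0.252.
- Its median absolute size is 0.6745 × 0.252 = 0.170 SD. It exceeds 0.5 SD with probability 0.047.
- At r = 0.3, the median imbalance moves the estimate by 0.3 × 0.170 = 0.051 SD, or 0.051/0.252 = 0.20 of its standard error.
- A 0.5 SD imbalance moves it by 0.3 × 0.5 = 0.15 SD, or 0.60 of a standard error.

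These shifts are part of the sampling variation that the unadjusted standard error measures, so the interval covers them on average.

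**3. What would adjustment do to precision?** For q covariates the expected variance ratio, adjusted to unadjusted, is (1 - r²)(N - 3)/(N - q - 3). With N = 63 and q = 2 this is (1 - r²) × 60/58. The interval-width ratio is its square root times t(59)/t(61) = 2.0010/1.9996. Power is from the noncentral t at a standardised difference of 0.6, where the unadjusted value is 64.9%.

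| Joint r | Change in 95% CI width | Power of the adjusted test, d = 0.6 |
|---|---|---|
| 0 | +1.8% | 63.4% |
| 0.2 | -0.3% | 65.2% |
| 0.3 | -2.9% | 67.5% |
| 0.4 | -6.7% | 71.0% |
| 0.5 | -11.9% | 75.8% |

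The width breaks even where (1 - r²) × (60/58) × (2.0010/1.9996)² = 1, which gives r of about 0.19. Below that, adjustment widens the interval. Nothing in the documents shows on which side of 0.19 these covariates fall, and the answer may differ across the four outcomes.

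**4. Would those power gains reach the trial's test?** No. The SAP says the ANOVA has been carried out. An adjusted model added now would be chosen after the fact and could properly serve only as a labelled sensitivity estimate carrying no new significance claim. The main test would keep its 64.9% at d = 0.6 whatever r is. Only the interval-width column describes what such an analysis could offer, and for r from 0 to 0.3 that is +1.8% to -2.9%.

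**5. Are these clean baseline covariates?** Vocabulary is not: it was self-completed after the clip and the speech task, so using it requires assuming that a 10-minute clip does not affect it. Age cannot be affected by the clip, but an inclusion criterion limits its range, and it may explain little. Education and gender were collected too, and the documents give no reason to prefer age over either.

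**The case for a change.** The strongest opposing case is that the cost and benefit are unequal. Adjustment uses two degrees of freedom. At d = 0.6 it loses at most 64.9 - 63.4 = 1.5 power points if the covariates explain nothing, against a gain of 75.8 - 64.9 = 10.9 points if they reach a joint r of 0.5. The data are already held, a vocabulary score is unlikely to be changed by a short clip, and a table of vocabulary and age by arm would let readers see whether this sample is unbalanced.

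The facts behind this stand: the model has no covariate, both variables are collected, and the arithmetic is right. A by-arm table would be useful description. The argument from power does not carry over, because those points belong to a test that should support no new claim once the main analysis has been run. The upper end of the range also rests on a correlation of 0.5 that nothing in the documents supports.

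The lack of a pre-clip speech sample is a real feature of the design, but adjusting for vocabulary and age does not supply one. Nor can it be concluded that the two variables go unused. The available Protocol text opens at Materials and mentions the age criterion as though already introduced, so a description of participants may exist elsewhere.

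**Conclusion.** The concern does not hold. Under random assignment the specified mixed ANOVA gives a valid test of condition, and nothing in the two documents contradicts it. An adjusted estimate would change interval width by between +1.8% and -11.9% for assumed joint correlations of 0 to 0.5, and would lose precision below about 0.19. It would be post hoc, would rely partly on a covariate measured after the intervention, and would alter neither the main test nor its conclusion. Statisticians could reasonably differ on whether to report it.

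Validity rests on the stated random assignment. The figures also assume complete data and roughly normal participant means; the filler and disfluency proportions come from short descriptions and may be skewed, so the percentages are illustrative.
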